Low-level light therapy (LLLT) and intense pulsed light (IPL) have gained traction as adjunctive treatments for MGD. Both therapies aim to improve meibomian gland function by reducing inflammation, improving glandular secretion, and decreasing Demodex mite counts Previous Studies suggest that combining LLLT and IPL with conventional therapies for MGD and blepharitis can lead to better clinical outcomes than monotherapy. However, limited research has evaluated the specific impact of these therapies on meibomian gland structure, especially when assessed using AI-assisted meibography

Our study aims to fill this gap by comparing pre- and post-treatment meibomian gland parameters in patients with Demodex blepharitis, using AI-assisted meibography to evaluate the effectiveness of LLLT, IPL, and combined treatments. By leveraging AI technology, this research intends to offer more objective and quantifiable insights into the impact of these treatments on meibomian gland health, which could ultimately improve patient outcomes in MGD management.

4.7) AI-Assisted Meibography Analysis: Our study plans to utilize an AI-assisted meibography developed system (18) to evaluate and compare the severity of meibomian gland dysfunction before and after low-level light therapy (LLLT) treatment for Demodex blepharitis. What sets this study apart is the integration of advanced AI-driven image analysis, specifically designed to assess the effectiveness of light-based therapies, which are playing an increasingly significant role in the treatment of meibomian gland dysfunction. This novel approach allows for precise, quantitative evaluation of treatment outcomes, offering a cutting-edge method to measure improvements in gland function.

5. Objectives

Study objectives to fulfill the knowledge gap

Primary objective:

To evaluate and compare the efficacy of mechanical with pharmacological treatment, LLLT, IPL and IPL + LLLT with Demodex Mite Count in MGD-related Demodex Blepharitis

Secondary objectives:

To evaluate and compare efficacy of mechanical with pharmacological treatment LLLT, IPL, IPL + LLLT for ocular surface parameters in MGD-related Demodex Blepharitis

6. Hypothesis

Null Hypothesis (H0):

There is no significant difference in the reduction of Demodex mite count among patients with Demodex Blepharitis treated with Low Level Light Therapy (LLLT), Intense Pulse Light Therapy (IPL), Combined LLLT + IPL, and Mechanical with pharmacological Treatment.

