2. Poor compliance with eyelid scrubbing using tea tree oil (TTO)
3. Dead demodex mite on lash.
4. Contraindication of IPL: Skin Fitzpatrick scale V/VI, patients with pigmented lesions on the treatment area (Eyelid, Cheek).
5. Pregnancy or breastfeeding.
6. Active Skin disease: facial skin cancer, graft-versus-host disease, systemic lupus erythaematosus
7. Active eye infection: recurrent herpes simplex
8. Other lid disease ocular trauma, ocular deformity scar, exophthalmos, eyelid insufficiency
9. Patients with pigmented lesion on area of treatment.

We will use computer-generated random number allocation into 4 groups in a 1:1:1:1 ratio including seed number, with the outcome assessor blind and participant blind with allocation concealment:

- 1.) ShamLLLT + ShamIPL
- 2.) LLLT + ShamIPL
- 3.) IPL + ShamLLLT
- 4.) LLLT + IPL

***All groups receive mechanical with pharmacological treatment (Warm compression + Lid hygiene + 1% TTO) for 90 days with google form logbook for record compliance and prevent co-interventional treatments.

***All group with participant/investigator/interpreter blind.

Blinding and Allocation Concealment in Research Team:

1st Research Assistant : Allocates patients according to computer-generated random number allocation, ensuring allocation concealment, Evaluated VA , IOP , OSDI score by reads the questionnaire to the participant

2nd Research Assistant (The treatment administrator) : Administers IPL, LLLT, or sham treatments.

3rd Research Assistant : Conducts assessments using Keratograph and Lipiview2.

Main Researcher : Evaluates primary and secondary outcomes using case record forms, remaining blind to the treatment groups.

Intervention Description

Mechanical with pharmacological treatment : Warm compression 15 minutes + Lid hygiene + 1% TTO for 90 days

1%TTO : OCuSOFT Oust Demodex Eyelid Cleanser Foam Bottle 50ml (OCuSOFT, Richmond, TX) is the only commercially available medication in Thailand that contains 1% tea tree oil.

IPL : The Eye-light device (Espansione Marketing S.p.A., Bologna, Italy, waveleggths 1,200-1,500 nm, Delivery system 12cm²) (Thai FDA No 66-2-2-0012685) :

- Protective eye shields
- 5 flashes of light were applied for each eye (3 along the inferior orbital rim, 1 at the lateral canthus, and 1 applied horizontally along the inferior orbital rim)
- Therapeutic energy level (10–16 joules/ cm²) based on the degree of skin pigmentation.

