For outcome ,Continuous data : Meibomian gland area ratio, Meibomian gland length and width,Meibomian gland diameter deformation index ,Meibomian gland tortuosity index, Meibomian gland signal index should be analyzed using ANOVA, while binary outcomes and ordinal data Meibomian gland dysfunction staging (severity) should be assessed using the chi-square test.

Any unavailable data will be treated as missing and will not be included in any calculations. The report will specify the percentage of missing data in each category. Statistical significance will be determined by a p-value < 0.05.

12.Ethical Consideration

The submission of the research proposal to the Institutional Review Board on Human Research at the Faculty of Medicine, Chulalongkorn University marks a pivotal step in ensuring the ethical oversight and approval of the prospective Randomized Control Trial (RCT)

Respect for Person:

Informed Consent: The principle of respect for persons underscores the importance of obtaining informed consent. Ensuring that participants have a clear understanding of the study's purpose, procedures, potential risks, and benefits is crucial.

Researchers employ transparent and comprehensive communication in the informed consent process, elucidating the randomization process, details of each intervention, and the freedom to withdraw at any point without repercussions.

Researchers will provide comprehensive information to ensure that volunteers understand the research well and make independent decisions regarding participation, without coercion or undue influence. If volunteers have legal representatives or proxies, they will be the ones reviewing the informed consent document and providing witness signatures. Researchers will seek permission from the hospital director at Chulalongkorn Hospital and will anonymize data using codes without disclosing patients' names, surnames, or hospital identification numbers.

Beneficence/Non-maleficence:

Risk-Benefit Assessment: Ethical research necessitates a careful evaluation of potential benefits against risks. Researchers must strive to maximize the positive outcomes of the study while minimizing any harm to participants.

Continuous monitoring of the interventions for unexpected risks and a commitment to modify or halt the trial if harms outweigh benefits are imperative to uphold the principles of beneficence and non-maleficence.

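### The ANOVA for the AI gland measures has no baseline term and no stated response; ANCOVA on baseline data already scheduled would be more precise at no cost

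*Combined protocol and SAP*

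**What the plan says.** For the continuous AI measures (area ratio, length, width, deformation, tortuosity and signal index), the whole analysis plan is one clause in section 11: "Meibomian gland signal index should be analyzed using ANOVA". No response variable, baseline covariate, factor structure or week is given. AI staging is handled apart: "ordinal data Meibomian gland dysfunction staging (severity) should be assessed using the chi-square test".

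Section 10 schedules data collection before treatment (within 0-14 days) and at weeks 8 and 16. The background text before section 4 also speaks of meibography photographs taken both before and after treatment.

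Two parts of the document describe the purpose differently:
- Section 4.6 speaks of "comparing pre- and post-treatment meibomian gland parameters in patients with Demodex blepharitis", "using AI-assisted meibography to evaluate the effectiveness of LLLT, IPL, and combined treatments". Section 4.7 speaks of severity "before and after low-level light therapy (LLLT) treatment for Demodex blepharitis".
- The secondary objective in section 5 is comparative: "To evaluate and compare efficacy of mechanical with pharmacological treatment LLLT, IPL, IPL + LLLT for ocular surface parameters".

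In section 9 the trial has a concurrent control arm, "ShamLLLT + ShamIPL", and background care is common to all four arms: "All groups receive mechanical with pharmacological treatment (Warm compression + Lid hygiene + 1% TTO) for 90 days".

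**The concern.** There are two separate questions, and each depends on how the plan is read.

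**Precision.** If the ANOVA is run on follow-up values alone, differences between patients that were present before treatment stay in the error term. The baseline reading that could remove them is collected but not used. With a planned 18 evaluable patients per arm, that waste would matter.

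**Attribution.** Sections 4.6 and 4.7 link effectiveness to a before/after comparison. Each light arm also receives 90 days of compresses, lid cleaning and tea tree oil. A within-arm change therefore mixes any light effect with background care, natural course and regression to the mean. If such a change were tested and reported as efficacy, the claim could be false even with no light effect.

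**Working it through.** **Inputs from the documents.** Four arms at 1:1:1:1 (section 9); 18 evaluable per arm and two-sided 5% (section 11). The 18 comes from the mite-count calculation. The plan gives no sample size, SD, effect or power for the gland measures, so it has no figure of its own to reproduce here.

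**Assumed inputs (not in the documents).** Baseline/follow-up correlation r = 0.5, 0.7 or 0.9; equal SD at baseline and follow-up; a between-arm effect of 0.5 SD for illustration; a shift common to all arms of 0.2, 0.3 or 0.5 SD.

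**Step 1: error variance relative to a follow-up-only ANOVA.**
- Follow-up value only: 1
- Change score: 2(1 - r)
- ANCOVA on baseline: 1 - r²

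The patients needed, relative to ANCOVA, are 1/(1 - r²) for follow-up only and 2(1 - r)/(1 - r²) = 2/(1 + r) for change.

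| r | ANCOVA variance | Change variance | Patients, follow-up only vs ANCOVA | Patients, change vs ANCOVA |
|---|---|---|---|---|
| 0.5 | 0.75 | 1.00 | 1.33 | 1.33 |
| 0.7 | 0.51 | 0.60 | 1.96 | 1.18 |
| 0.9 | 0.19 | 0.20 | 5.26 | 1.05 |

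At r = 0, ANCOVA gains nothing over follow-up values, while change scores have twice the variance. ANCOVA is never worse than either, apart from one degree of freedom.

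**Step 2: what this means at 18 per arm.** For a pairwise contrast, power is approximately Φ(0.5/√(2v/18) - 1.96), where v is the variance factor from step 1.
- Follow-up only, v = 1: 0.5/0.333 = 1.50, so Φ(-0.46) = 32%.
- Change, v = 1.00, 0.60, 0.20: 32%, 49%, 92%.
- ANCOVA, v = 0.75, 0.51, 0.19: 41%, 56%, 93%.

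**Step 3: the attribution risk, if a within-arm test were done.** Suppose light does nothing and every arm shifts by s SD. A paired t test in one light arm of 18 has noncentrality s√18/√(2(1 - r)), 17 degrees of freedom and critical value 2.110. For s = 0.3 the noncentrality is 1.27, 1.64 and 2.85.

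| Common shift s | r = 0.5 | r = 0.7 | r = 0.9 |
|---|---|---|---|
| 0.2 SD | 13% | 18% | 43% |
| 0.3 SD | 22% | 34% | 77% |
| 0.5 SD | 52% | 73% | 99% |

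These are the chances of a significant before/after result with no light effect. In a contrast with the double-sham arm the common shift s appears on both sides and cancels, so the error rate stays at 5%.

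**The case against.** The strongest reply is that section 11 does not say the ANOVA leaves out the baseline. Its response is unstated. Read together with section 4.6, it could well mean a between-arm ANOVA of change. Under that reading background care cancels, and the gain from ANCOVA is the modest 1.33, 1.18 or 1.05 times, not up to 5.26. This stands, and the larger figures apply only if follow-up values are analysed alone.

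A reader might also infer that the plan will credit background improvement to light. The documents do not support that as a statement of what is planned. The before/after wording sits in the literature review, section 11 contains no paired or within-arm test, the secondary objective is comparative and a double-sham arm is randomised alongside. The percentages in step 3 describe a test the plan never specifies.

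Nor can one infer that the ANOVA is biased, because omitting baseline from a randomised comparison costs precision only. Low power is also largely a matter of sample size: at r = 0.5 or 0.7 ANCOVA still reaches only 41% or 56% for the assumed effect. Finally, the correlations and the common shift are assumptions, and no figure in the documents shows how stable gland structure is within a patient.

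None of this removes the point. Both readings of the ANOVA are open, and ANCOVA is at least as precise under each.

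**Conclusion.** The point holds as a free improvement in precision, with a related inconsistency in wording. Section 11 leaves the response and baseline handling of the continuous gland measures open. ANCOVA would save between 5% of the patients (1 - 1/1.05, change scores at r = 0.9) and 81% (1 - 1/5.26, follow-up values at r = 0.9), and 25% under either reading at r = 0.5. These sizes rest on the assumed correlations, and at r near zero there is no gain over a follow-up-only analysis.

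The attribution risk is conditional: it arises only if the before/after wording of sections 4.6 and 4.7 becomes the basis for inference. The mite count is not affected by this point.

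**What to change.** 1. In section 11, replace ANOVA for the continuous gland measures with ANCOVA: the follow-up value at one stated week, regressed on LLLT, IPL, LLLT x IPL and the patient's own baseline value of the same measure.
2. State that effectiveness is judged only between randomised arms, and that within-arm before/after change is reported descriptively, without p-values.
3. Align sections 4.6 and 4.7 with that statement and with the secondary objective.
4. Optionally, use the same model for the other continuous secondary outcomes measured at baseline, such as OSDI, NIBUT, tear meniscus height, lipid layer thickness and percentage gland loss. Section 11 names no test for these.

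The cost is wording only. Baseline data collection is already scheduled, and no visit, measurement or patient is added.

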Evaporative dry eye in dry eye disease (DED) is a long-term, multifactorial condition affecting the tears and the ocular surface, with a huge worldwide impact. It encompasses two main types: aqueous deficient and evaporative dry eye(15). In the USA, DED incurs an indirect annual cost of US \$73.12 billion, equating to US \$15,596 per person, due to diminished productivity(16). Treatment costs vary by DED severity, ranging from US \$300 to US \$1100 per person across different countries (17). The global DED market, valued at USD 5.22 billion in 2019, is anticipated to reach USD 6.54 billion by 2027, with an annual growth rate of 4.7%.

Beyond financial concerns, various studies highlight DED as a burdensome condition associated with depression, which is a hidden problem often overlooked.

Artificial intelligent technology has revolutionized the field of ophthalmology, particularly in the analysis of meibomian gland images. By incorporating AI-based meibography, we can improve the accuracy and consistency of assessments related to glandular health, a crucial factor in managing MGD associated with Demodex blepharitis. Yuan et al. (2021) have demonstrated a reliable AI-based methodology for normalizing and segmenting meibomian gland images, offering substantial advancements over conventional techniques(18)

Our study pioneers a Factorial Randomized Control Trial (RCT) investigating Low-Level Laser Therapy (LLLT) for the treatment of demodex blepharitis, comparing it with Intense Pulsed Light (IPL), IPL combined with LLLT, and mechanical with pharmacological approaches. The aim is to address the limitations of mechanical with pharmacological treatment for demodex blepharitis, particularly in terms of the efficacy of innovative laser treatments, improved compliance, and reduced disease burden, ultimately leading to better treatment outcomes and

used AI-based meibography to evaluate the meibography photos which taken from demodex blepharitis patient before and after treatment.

Novel questions

1.Will Low-Level Light Therapy (LLLT) and/or Intense Pulsed Light (IPL) therapy synergistically or antagonistically improve the mean reduction of Demodex mite count in patients with Demodex blepharitis?

2.Will Low-Level Light Therapy (LLLT) and/or Intense Pulsed Light (IPL) therapy synergistically or antagonistically improve the Meibomian Gland Dysfunction (MGD) stage in patients with Demodex blepharitis?

4. Literature Review

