Alternative Hypothesis (H1):

There is a significant difference in the reduction of Demodex mite count among patients with Demodex Blepharitis treated with at least one of the following therapies: Low Level Light Therapy (LLLT), Intense Pulse Light Therapy (IPL), Combined LLLT + IPL, greater than Mechanical with pharmacological Treatment.

[figure not shown]
Hypotheses

- LLLT or IPL, will be equally effective in reducing Demodex mite count and improving ocular surface parameters.
- IPL + LLLT will be more effective than LLLT or IPL alone in reducing Demodex mite count and improving ocular surface parameters.

7. Keywords

Demodex blepharitis, MGD, LLLT, IPL, Demodex mite count, Demodex mite eradication, Ocular surface parameters

Conceptual framework

Variables

Independent variables:

the different treatment modalities:

- 1.Low Level Light Therapy (LLLT)
- 2.Intense Pulse Light Therapy (IPL)
- 3.Combined LLLT + IPL
- 4.Mechanical with pharmacological treatment

Dependent variables: Mean Demodex Count, MGD Staging, OSDI Questionnaire, Meibum Quality, Meibum Expressibility, Telangiectasia Grading (0-3), Surface Staining (NEI Grading System), % Meibomian Gland Loss (MGL), Lipid Layer Thickness, Noninvasive Break-Up Time (NIBUT), Tear Meniscus Height (TMH),

8. Research Design

Single Center, 2x2 Factorial Randomized Control Trials

9. Research Methodology

Target Population: Demodex blepharitis patients at the Department of Ophthalmology, King Chulalongkorn Memorial Hospital.

This is a single-center, prospective, 2x2 factorial Randomized Control Trials involving outpatients with Demodex blepharitis presenting at the Department of Ophthalmology, King Chulalongkorn Memorial Hospital (KCMH) from Nov 2024 to Nov 2025.

The approach to participants: involves patients under the care of the research physician. They are recruited through advertisements and contacted through the patient's physician to introduce the researcher and seek volunteer participation.

The inclusion criteria consist of:

1. All patients who received a definite diagnosis of demodex blepharitis based on cylindrical dandruff at the base of the lashes and the presence of at least one alive demodex mites on eyelid margin by microscopy
2. Age >18 years.
3. Patients who can understand and follow the study instructions and can adhere to the scheduled follow-up plan.

The exclusion criteria consist of:

1. Patients who received previous treatment IPL or LLLT

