LLLT : The blue MY MASK-E (Espansione Marketing S.p.A., Bologna, Italy) (Thai FDA No 66-2-2-0012685)

- No eye shields
- Applying a special mask for 15 minutes, once a week for 4 weeks

ShamLLT : the MY MASK-E (Espansione Marketing S.p.A., Bologna, Italy) – No eye shields, applying a power off special mask for 15 minutes , once a week for 4 weeks

ShamIPL : the Eye-light device (Espansione Marketing S.p.A., Bologna, Italy) - Protective eye shields, 5 time for each eye with flashes of light off.

Epilation Strategies

the Modified Coston method as outlined by Gao et al. in 2005. In this method, two lashes containing cylindrical dandruff (CD) then additional **rotated around itself** were extracted from each eyelid of every participant using fine forceps. These lashes were then individually placed at opposite ends of a glass slide for observation under a slit-lamp biomicroscope (SL220; Carl Zeiss, Oberkochen, Germany) at a magnification of $\times 25$. This process resulted in four lashes of right eye being prepared across two slides for each participant. A coverslip was applied to each lash, followed by the slow pipetting of 20 μL of saline at the coverslip's edge until it surrounded the lash. Subsequently, 20 μL of 100% alcohol was pipetted at the same edge, extending the counting period for up to 20 minutes to facilitate the migration of embedded Demodex from the CD. The Demodex count was performed thrice under the microscope, and all samples were photographed using standard procedures by the same specialist. The presence of Demodex in at least one of the eight eyelashes was considered Demodex-positive

10. Data Collection:

Primary Outcome:

Mean of Demodex Count - the number of Demodex mites per eyelash on a total of 4 collarettes lashes epilation (2 from upper eyelid ,2 from lower eyelid and identification by anatomical imaginary line of nasal and temporal limbus) per right eye in 30 days after end of treatment. (8th week)

Secondary Outcomes:

1.Mean of Demodex Count - per right eye in 90 days after end of treatment.(16th week)

2.MGD staging (Severity)

[figure not shown]
OSDI questionnaire used to evaluate ocular dry eye symptoms.

OCULAR SURFACE DISEASE INDEX®					
Please answer the following questions by checking the box that best represents your answer.					
Have you experienced any of the following during the last week:					

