A score of 100 corresponds to complete disability (a response of "all of the time" to all questions answered), while a score of 0 corresponds to no disability (a response of "none of the time" to all questions answered). Therefore, change from baseline of -12.5 corresponds to an improvement by at least one category in half of the questions answered.					
Subscale Scoring					
Subscales scores are computed similarly with only the questions from each subscale used to generate its own score. Therefore, any subscales analyzed separately would also have a maximum possible score of 100.					
The three subscales (vision-related function, ocular symptoms and environmental triggers) are broken out as follows:					
Subscale	Questions				
Vision-Related Function	4, 5, 6, 7, 8, 9				
Ocular Symptoms	1, 2, 3				
Environmental Triggers	10, 11, 12				

Meibum Quality.

Meibum Expressibility.

[figure not shown]
Telangiectasia grading: 0-3

3.Surface Staining: NEI Grading System.

4.Lipid Layer Thickness by LIPIVIEW

5.Noninvasive break-up time (NIBUT), tear meniscus height (TMH) , % Meibomian Gland Loss (MGL) by Keratograph 5M (OCULUS, Germany)

6.Corrected one times baseline , including BCVA, IOP.

7. After complete datacorrection : Meibography images will be masked and analyzed using an AI-assisted program to assess the following:

- Meibomian gland dysfunction staging (severity): MGD severity level and scored with 1-5 according to the 2011 MGD workshop (27) (Figure1)
- Meibomian gland area ratio: The proportion of the total visible meibomian gland area to the overall tarsal area in the eyelid
- Meibomian gland length: The linear measurement from the proximal to distal end of a meibomian gland, reflecting its elongation or shortening due to disease.
- Meibomian gland width: The horizontal width of individual meibomian glands, which helps assess gland atrophy or hypertrophy.

- Meibomian gland diameter deformation index: A metric for measuring irregularities in the shape and thickness of the glands, indicating glandular structural deformation.
- Meibomian gland tortuosity index: A measure of the curvature or twisting of the meibomian glands, used to assess changes in gland architecture.

Meibomian gland signal index: The intensity or brightness of the meibomian gland signal in meibography images, indicating gland density and activity

Visiting schedule:

1st visit	- Before treatment within 0-14 days (1 st Data correction+Epilation)

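### MGD stage, an ordered secondary outcome, is assigned only a chi-square test, which ignores stage order and gives no formal test or estimate for novel question 2 (LLLT×IPL synergy on stage)

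*Combined protocol and SAP*

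**What the plan says.** Section 11 (statistical analysis, plan, and data management) sends the continuous gland measures to ANOVA and states that "ordinal data Meibomian gland dysfunction staging (severity) should be assessed using the chi-square test". No other analysis is named for this outcome. The documents contain no trend test, ordinal model, interaction term or baseline adjustment for it.

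The outcome is ordered. Section 10, item 7, describes it as "MGD severity level and scored with 1-5 according to the 2011 MGD workshop", and it appears among the secondary outcomes both in section 10 and in the Outcomes list after section 12.

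Novel question 2, just before section 4, asks whether the treatments will "synergistically or antagonistically improve the Meibomian Gland Dysfunction (MGD) stage in patients with Demodex blepharitis". Section 8 gives the design as "Single Center, 2x2 Factorial Randomized Control Trials", and section 9 lists the four sham-controlled arms. Section 4.7 intends to "compare the severity of meibomian gland dysfunction before and after low-level light therapy (LLLT) treatment", and the visiting schedule collects data before treatment and at weeks 8 and 16.

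**The concern.** The plan calls the outcome ordinal and then names a test that treats the stages as unordered categories. Two things are lost. The first is power, because treatment is expected to move patients along the scale. The second is direction: a significant p-value would not say whether stage improved or worsened, or whether the combination did more or less than the two separate effects predict. Synergy on stage is the whole of novel question 2, and the four arms provide exactly the contrast needed to estimate it. The named test also makes no stated use of baseline stage, despite the before-and-after comparison promised in section 4.7.

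**Working it through.** The plan states no sample size, power or effect for MGD stage, so there is no figure of its own to reproduce. The check has three parts.

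**1. What the test can see.** This part needs no assumption about effect size. Take an invented table with 18 per arm: sham, LLLT alone and IPL alone each have 2/3/5/5/3 patients in stages 1 to 5, and the combination has 7/6/3/1/1. The column totals are 13, 15, 18, 16 and 10, so the expected counts in every arm are 3.25, 3.75, 4.5, 4 and 2.5. The sum of (observed − expected)²/expected, by column, is

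18.75/3.25 + 6.75/3.75 + 3/4.5 + 12/4 + 3/2.5 = 5.77 + 1.80 + 0.67 + 3.00 + 1.20 = 12.44

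on (4−1)(5−1) = 12 df, giving p = 0.41. Reversing the stages or swapping arms only reorders the same terms, so the result is unchanged. A proportional-odds model with LLLT, IPL and LLLT×IPL gives an interaction of −1.77 (SE 0.86, Wald p = 0.04) on the log-odds scale. With the stages reversed it gives +1.77. The table was built to show this invariance, so its p-values do not indicate a typical gain.

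**2. Power lost by ignoring order.** From the documents: 18 evaluable patients per arm (section 11), five stages, 5% level. Assumed: stages evenly distributed under control, a proportional-odds shift with odds ratio 2, 3 or 4, one treatment active, no baseline term. Relative loss = (rank-test power − chi-square power)/rank-test power.

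| Layout | Chi-square, OR 2/3/4 | Rank test, OR 2/3/4 | Loss |
|---|---|---|---|
| 4 arms × 5 stages | 13/31/45% | 22/55/75% (Kruskal-Wallis) | 9/22 = 41%, 24/55 = 44%, 30/75 = 40% |
| One factor, 2 × 5 | 20.5/51/72% | 36/74/88% (two-group) | 15.5/36 = 43%, 23/74 = 31%, 16/88 = 18% |

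A separate 4×5 run of 4,000 trials per setting gave 12.5/28.5/47.3% against 23.5/53.7/75.8%, a loss of 47/47/38%, so these figures carry simulation error of a few points. With both treatments active, the 4×5 comparison was 23.3/56.0/76.8% against 44.6/82.1/95.2%, a loss of 48/32/19%.

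A third possible layout is improved versus not improved, which uses baseline indirectly. With one active treatment and an assumed baseline correlation of 0.5 it reached 14.8/29.9/45.3%, so it does not recover the power. None of the three layouts tests an interaction.

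**3. Type I error and what the interaction model can deliver.** The mean expected count in a 4×5 table is 72/20 = 3.6, or 88/20 = 4.4 with 22 per arm. Under the null the chi-square nevertheless rejected in 3.8–4.9% of simulated trials, so it is not liberal. Power for the interaction term at interaction OR 2/3/4 was 16.5/31.9/44.5% with 18 per arm and 18.3/37.9/53.0% with 22. The Wald tests rejected in 5.2–6.2% under the null.

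**The case against.** The formal objectives and the null hypothesis (sections 5 and 6) compare four treatments. An omnibus chi-square does address that comparison, and it is valid. This stands. A reader might infer that the planned stage result would be wrong or a false positive, but nothing in the documents or the checks supports that.

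The stage counts by arm already show direction descriptively. This also stands: with interaction OR 3 and no main effects, a plain contrast of mean stages had the right sign in about 90% of simulated trials. What the model adds is an effect size, an interval and a test.

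Section 11 does not state a table layout, and a per-factor 2×5 table is natural in a factorial trial. This narrows the loss for larger effects but does not remove it. At OR 2 a loss of about 40% is only 9 to 16 percentage points, and both tests are weak.

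The missing interaction is not special to MGD stage: section 11 names none for any outcome. That is true and limits what is particular here. The disregard of stage order is specific to this outcome.

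Finally, the interaction is underpowered under any analysis. A reader might infer that an ordinal model would settle question 2. At this sample size it would not.

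**Conclusion.** The point holds as a mismatch between a stated method and a stated question. The chi-square discards the order of an outcome that the plan itself calls ordinal, and it leaves novel question 2 without a formal test or estimate. That conclusion is a property of the test and rests on no assumed effect.

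The size of the power loss does rest on assumptions. With even stages, 18 per arm, OR 2 to 4 and one active treatment, it is about 40–45% in a 4×5 table and about 18–43% in a per-factor 2×5 table. The documents supply no stage distribution, effect size or layout that would narrow this.

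The scope is also uncertain. The measures listed in section 11 match those in section 10, item 7, which begins "Meibography images will be masked and analyzed using an AI-assisted program to assess the following". The sentence may therefore cover only the AI-read stage, in which case the clinically graded stage has no named test.

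The change should be made, but the matter is confined to a secondary outcome and does not touch the primary mite count.

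**What to change.** Replace the chi-square for MGD stage with wording such as:

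> MGD stage will be analysed by ordinal (proportional-odds) regression on LLLT, IPL, LLLT×IPL and baseline stage. Odds ratios for both main effects and the interaction will be reported with 95% confidence intervals, with stage counts by arm. If the model cannot be fitted, each main effect will be tested by a rank test stratified by the other factor.

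State which reading (AI-read or clinically graded) and which visit (week 8 or week 16) answer question 2, and treat the others as supportive. Otherwise 3 terms × 2 readings × 2 visits = 12 tests would compete at p < 0.05. Say in advance that interaction power is low, so the result is a signed estimate with its interval.

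The cost is SAP wording and modest extra analysis. The baseline, week-8 and week-16 collections are already scheduled, so no new patients or data are needed. Section 10 names SPSS, so confirm that the chosen model runs there. Other downsides are the proportional-odds assumption, slightly liberal Wald tests at this size, and a fallback that covers main effects only. In simulation the model failed to converge in at most 2.1% of trials (both treatments active, OR 4), so the fallback should seldom be needed.
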